4.7.3. Assessment of Accumulation Ratio

To assess the extent of accumulation following mepolizumab multiple doses, the observed accumulation ratio (Ro) for mepolizumab will be determined as ratio of Cmax_ss (Cmax observed after last dose) to Cmax (Cmax observed after the first dose) and ratio of Ctrough_ss (Ctrough before the last dose) to Ctrough (Ctrough after the first dose)

$$Ro(Cmax) = Cmax_ss / Cmax$$

$$Ro(Ctrough) = Ctrough_ss / Ctrough$$

Accumulation ratios of Cmax and Ctrough will be summarised using n, mean, 95% confidence interval for the mean, standard deviation, median, minimum, maximum, between coefficient of variation, geometric mean, 95% confidence interval for the geometric mean and standard deviation of log-transformed data, and listed.

This pharmacokinetic statistical analysis will only be performed if sufficient data are available.

4.7.4. Population Pharmacokinetic or Pharmacokinetic/Pharmacodynamic Analysis

If deemed necessary, the pharmacokinetic and/or pharmacodynamic data collected from the study may be combined with data from other studies for a population pharmacokinetic or pharmacokinetic/pharmacodynamic analyses. In that case, an analysis plan will be prepared independently. All eligible pharmacokinetic or pharmacodynamic data collected from the study will be included into the analyses.

4.8. Interim Analyses

No formal interim analysis is planned.

4.9. Changes to Protocol Defined Analyses

There were no changes or deviations to the originally planned statistical analysis specified in the protocol amendment 04 (Dated: [18-NOV-2021]).

5. SAMPLE SIZE DETERMINATION

5.1. Sample Size Assumptions

The sample size of 300 participants (considering 256 evaluable participants and additional 44 subjects for drop-out) in a 1:1 ratio has been determined by the superiority testing of mepolizumab 100 mg SC vs. placebo, there will be 90% power to detect a 40% decrease in the exacerbation rate from 1.7 per annum (p.a.) on placebo to 1.02 p.a. on mepolizumab 100mg SC using a two sided 5% significance level. The calculation assumes the number of exacerbations per year follows a negative binomial distribution [Keene, 2007] with a dispersion parameter $k=0.8$.

During the blinded evaluation, the clinically significant exacerbations occurred during the treatment period were analyzed using a generalized linear model assuming a negative binomial distribution and covariates of baseline maintenance OCS therapy (OCS vs. no OCS), EOS level at screening ($>=300$ cells/ μ L vs. <300 cells/ μ L), number of exacerbations in previous year (as an ordinal variable) and baseline disease severity (as % predicted FEV1). The blinded evaluation concluded, the overall event rate under blinded was observed as 0.78 p.a., the dispersion was 2.0.

This reduction observed for overall events at blinded evaluation can be explained by a reduction in exacerbation events during the COVID-19 pandemic, which was not unique in China. , it is still expected that the treatment effect of Mepolizumab compared with placebo will be the same in Chinese SEA population as the original assumption. Therefore, according to the formula [Friede, 2010]

$$\bar{\lambda} = (\lambda_T + \lambda_P)/2$$

where $\bar{\lambda}$ is the overall events rate under blinded, the λ_T and λ_P are the event rates in the treatment and placebo groups, and assuming the reduction will keep the same as 40% under pandemic, the estimated event rates λ_T and λ_P for Mepolizumab 100mg SC and placebo are 0.585 and 0.975 p.a. respectively. On the other hand, there exists a difference for the estimate of dispersion when data is blinded or unblinded, so that the dispersion is adjusted by the difference between blinded and unblinded, which is $1.6=2.0 * (0.796 / 0.972)$, where the dispersion in MEA115588 study were 0.796 (unblinded) vs. 0.972 (blinded).

Therefore, based on the conclusion on blinded evaluation, assuming a 40% decrease in the exacerbation rate from 0.975 per annum (p.a.) on placebo to 0.585 p.a. on mepolizumab 100mg SC, they will lead to a power of 66% implying a high false negative rate of 34% in China study. If there is a true reduction of 40% in exacerbation rate in Chinese patients, based on use of Bayesian dynamic borrowing with an initial weight of 0.5 on global MEA115588 study result, there will be 88.6% probability to achieve a positive result (equivalent to the power of the study).

The 40% reduction in exacerbation rate has been selected as reductions of this magnitude or greater have been seen in previous mepolizumab studies MEA112997 and MEA115588. However, it should be noted that a smaller reduction in exacerbations could

be clinically significant. Under the same assumptions, there will be 99% probability of showing consistent trend, which is defined as the point estimation of rate ratio between Mepolizumab and placebo<1 in China study, with global MEA115588.

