9.2. Sample Size Determination

9.2.1. Sample Size Assumptions

The sample size of 300 participants (considering 256 evaluable participants and additional 44 subjects for drop-out) in a 1:1 ratio has been determined by the superiority testing of mepolizumab 100 mg SC vs. placebo, there will be 90% power to detect a 40% decrease in the exacerbation rate from 1.7 per annum (p.a.) on placebo to 1.02 p.a. on mepolizumab 100mg SC using a two sided 5% significance level. The calculation assumes the number of exacerbations per year follows a negative binomial distribution [Keene, 2007] with a dispersion parameter $k=0.8$.

During the blinded evaluation, the clinically significant exacerbations which had occurred during the treatment period were analyzed using a generalized linear model assuming a negative binomial distribution and covariates of baseline maintenance OCS therapy (OCS vs. no OCS), EOS level at screening (≥ 300 cells/ μ L vs. < 300 cells/ μ L), number of exacerbations in previous year (as an ordinal variable) and baseline disease severity (as % predicted FEV1). The blinded evaluation estimated, the overall event rate based on an assessment of blinded data was observed as 0.78 p.a., the dispersion was 2.0. This was lower than the expected overall event rate of the original study design assumptions.

This observed reduction for overall events at blinded evaluation can be explained by a reduction in exacerbation events during the COVID-19 pandemic, which was not unique in China, it is still expected that the treatment effect of Mepolizumab compared with placebo will be the same in Chinese SEA population as the original study design assumption. Therefore, according the formula [Friede, 2010]

$$\bar{\lambda} = (\lambda_T + \lambda_P)/2$$

where $\bar{\lambda}$ is the observed overall events rate based on an assement of blinded data, the λ_T and λ_P are the event rates in the treatment and placebo groups, and assuming the reduction in exacerbation rate with Mepolizumab will remain 40% under pandemic, the estimated event rates λ_T and λ_P for Mepolizumab 100mg SC and placebo are 0.975 and 0.585 p.a. respectively. On the other hand, there exists a difference for the estimate of dispersion when data is blinded or unblinded, so that the blinded dispersion estimate is adjusted by the difference between blinded and unblinded, which is $1.6=2.0 * (0.796 / 0.972)$, where the dispersion in MEA115588 study were 0.796 (unblinded) vs. 0.972 (blinded).

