The BDB approach will use the results from the global MEA115588 study mixed with a vague component worth two subjects as an ‘informative’ but robust prior for the treatment comparison of interest in this China study. There are two primary analysis comparisons: mepolizumab 75mg IV vs placebo and mepolizumab 100mg SC vs placebo for rate of clinically significant exacerbations over the 32 weeks treatment period expressed as exacerbation rate per year in MEA115588. Since the primary outcome, rate of clinically significant exacerbation, showed similar treatment difference in Mepolizumab 75 mg iv group compared with placebo in 32-week Study MEA115588 and 52-week Study MEA112997, this indicates the available efficacy result of Mepolizumab 100 mg SC in 32-week study MEA115588 could also be an informative reference data to bridge to this 52-week China study using the same dose regimen, therefore, the results of mepolizumab 100mg SC vs placebo in study MEA115588 are used to build the global component.

Table 8 The primary analysis of clinically significant exacerbations results in global MEA115588 study

Treatment	No. subjects	Rate ratio (95% CI)	Normal distribution of Rate Ratio (log)	
			Mean	Standard Error
Mepolizumab 100mg SC	194	0.47 (0.35,0.64)	-0.7474	0.1532
Placebo	191			

Source: Table 13 in the CSR of MEA115588.

The logarithmic transformation of the rate ratio will be used, which can be approximately Normally distributed. Therefore, in the primary analysis for the primary treatment comparison of mepolizumab 100mg SC and placebo for the rate of clinically significant exacerbations of asthma over the 52-week treatment period in this study, the global prior component is obtained from the sampling distribution of the log rate ratio between mepolizumab 100mg SC and placebo in the global study MEA115588. The mean log rate ratio and its associated standard error are -0.7474 and 0.1532, respectively, leading to a normal distribution with mean -0.7474 and standard deviation 0.1532 as the global prior component for the primary treatment comparison.

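### The blinded-to-unblinded dispersion conversion (2.0 to 1.6) is inconsistent with the 40% reduction assumed beside it; consistent values of about 1.82–1.88 put China-only power at 62–63%, not 66%

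*SAP*

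**What the plan says.** SAP 5.1 reports the blinded look as follows: "the overall event rate under blinded was observed as 0.78 p.a., the dispersion was 2.0". It then assumes that the 40% reduction still holds and splits the overall rate into arm rates; those for mepolizumab and "placebo are 0.585 and 0.975 p.a. respectively". For the dispersion it uses no effect assumption. It says that "the dispersion is adjusted by the difference between blinded and unblinded" and multiplies 2.0 by 0.796/0.972, the unblinded and blinded dispersions in MEA115588, to get 1.6. Protocol 9.2.1 has the same step: "the blinded dispersion estimate is adjusted by the difference between blinded and unblinded".

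The value 1.6 then feeds three sets of figures:

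- the China-only power, of which the SAP says "they will lead to a power of 66% implying a high false negative rate of 34% in China study";
- every column of SAP Table 2 and Protocol Table 7, which give success probabilities of 94.6%, 88.6%, 80.0% and 11.8% at reductions of 45%, 40%, 35% and 0;
- the maximum detectable rate ratio (MDV) of 0.776 in Protocol 9.4.1.

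On MEA115588, Protocol 9.4.1 says: "The mean log rate ratio and its associated standard error are -0.7474 and 0.1532, respectively". That is a rate ratio of 0.47.

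**The concern.** A blinded dispersion exceeds the within-arm value because pooling two arms with different rates adds variance. The excess depends on how far apart the arms are. MEA115588 had a 53% reduction, while the China calculation assumes 40%. Carrying over the MEA115588 ratio therefore removes more dispersion than a 40% effect could have added. The paragraph uses the 40% assumption for the rates and, in effect, a larger one for the dispersion.

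A dispersion that is too low gives a standard error that is too small. At stake are the published operating characteristics of an analysis changed during the trial: the power given as the reason for borrowing, the success probability described as equivalent to power, and the stated type I error. All of them err in the favourable direction.

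**Working it through.** **Inputs.** From SAP 5.1–5.2: overall rate 0.78, blinded dispersion 2.0, 128 per arm, two-sided 5%. From SAP 4.2.1: prior 0.5·N(−0.7474, 0.1532) + 0.5·N(0, 2.1256). From SAP 2: success if P(RR<1) is at least 95%. Assumption: one year of follow-up per evaluable subject. SAP 5.1 does not state this, but it reproduces the plan's figures.

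**1. Reproduce the plan at k = 1.6.** SE = √[(1/λP + 1/λT + 2k)/128].

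- Power at 40%: SE = √[(1/0.975 + 1/0.585 + 3.2)/128] = 0.2153. Power = Φ(0.5108/0.2153 − 1.96) = 66.0% (stated 66%).
- Success: apply the SAP 4.2.1 mixture update, find the observed log rate ratio m* at which P(RR<1) = 0.95, then compute Φ((m* − log RR)/SE). At 40%, exp(m*) = 0.776, the stated MDV. Success is 94.4%, 88.4%, 79.7% and 11.7%, within 0.3 points of the stated values.

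**2. Relate blinded to within-arm dispersion.** For a 1:1 mixture of two negative binomial arms with common k,

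k_blinded = (1+k)(1+d) − 1, with d = ((1−RR)/(1+RR))².

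At RR 0.60, d = (0.4/1.6)² = 0.0625.

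- Forward: k = 1.6 gives 2.6 × 1.0625 − 1 = 1.76. The maximum-likelihood (ML) limit of a single negative binomial fitted to the mixture is 1.72. Neither is 2.0.
- Backward: k = 3/1.0625 − 1 = 1.82 by moments. The ML limit gives 1.85 with a quarter-year of follow-up and 1.88 with one year.
- By moments, going from 2.0 to 1.6 needs 1 + d = 3/2.6, so d = 0.154 and RR is about 0.44, a 56% reduction.

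**3. Check against MEA115588.** With RR 0.47, d = (0.53/1.47)² = 0.130. With k = 0.796 the moment formula gives 1.796 × 1.130 − 1 = 1.03, and ML gives 0.99–1.00 (placebo rate 1.7 assumed). The reported value is 0.972, so the model is close but slightly high.

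**4. Solve each column.** Moment values are 3/(1+d) − 1, with d = 0.0843 at 45%, 0.0625 at 40%, 0.0450 at 35% and 0 at no effect. The upper end of each range is the one-year ML value.

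| True reduction | Consistent k | Success, stated | At k = 1.6 | At consistent k |
|---|---|---|---|---|
| 45% | 1.77–1.84 | 94.6% | 94.4% | 93.5–93.8% |
| 40% | 1.82–1.88 | 88.6% | 88.4% | 87.0–87.3% |
| 35% | 1.87–1.91 | 80.0% | 79.7% | 77.9–78.2% |
| 0 | 2.0 | 11.8% | 11.7% | 12.8% |

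At 40%, SE is 0.2233–0.2252 and China-only power is 62.8–62.1%. The MDV is 0.774–0.773. In the null column, SE = √[(2/0.78 + 4)/128] = 0.2265, the threshold is 0.773 and Φ(log 0.773/0.2265) = 12.8%. The 99% probability of a consistent trend becomes 98.8–98.9% and still rounds to 99%.

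**The case against.** The strongest reply has four parts.

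*The multiplication is disclosed and reproducible.* This is true. 2.0 × 0.796/0.972 = 1.638, shown as 1.6, and every downstream figure follows from 1.6. A reader might infer a computing slip. There is none beyond the rounding, which accounts for about 0.5 points of power (65.4% at 1.638). The fault lies in the conversion rule.

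*The blinded estimate is noisier than the correction.* This is also true. If the look had 225 subjects with either one year each or staggered follow-up, simulation gives a standard error for the blinded k of roughly 0.4–0.65, against a shift of 0.22–0.28. That argues for showing a range. It does not support a point value that contradicts the assumed effect.

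*The 44 additional subjects are left out, although they contribute partial exposure.* If 22 per arm contribute 0.25–0.5 year, power at k = 1.82–1.88 is about 65–68% and success at 40% about 88–89%, close to the stated values. This concerns the trial as run. The plan states its figures for 128 per arm, and adding the same subjects at k = 1.6 would raise those figures too.

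*No decision changes.* This stands. The analysis uses the observed estimate and standard error, so the design dispersion does not enter it. Lower China-only power slightly strengthens the stated reason for borrowing.

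A reader might also infer that the lower dispersion in MEA115588 is itself a main reason why the ratio does not carry over. By moments it is not: RR 0.47 with a blinded 2.0 gives k = 3/1.130 − 1 = 1.66, close to the plan's 1.638, so most of the gap is the effect size. ML leaves more room for the dispersion level (about 1.75), but the documents give too little to establish it as a separate cause.

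**Conclusion.** The conversion is inconsistent with the 40% reduction assumed in the same paragraph. On the plan's own basis the China-only power is 62–63%, 3 to 4 points below the stated 66%. The success probabilities are about 1–2 points lower than stated, part of which (0.2–0.3 points) is reproduction difference. The MDV falls by 0.002–0.003. The null column is affected as well: with no effect there is nothing to remove, so k stays at 2.0 and the false positive rate is about 12.8%, one point above the stated 11.8%.

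The result assumes a common dispersion in both arms, 1:1 allocation and one year of follow-up. Covariate adjustment in the blinded model leaves the conversion unchanged if the effect is constant across covariates. Exposure at the blinded look is not reported, hence the ranges. A reader might infer that the trial is undersized or that borrowing loses its justification; the figures support neither.

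**What to change.** In SAP 5.1 and Protocol 9.2.1, replace the MEA115588 ratio by solving (1+k)(1+d) − 1 = 2.0, or its ML equivalent, at each assumed reduction. Apply this to every column of SAP Table 2 and Protocol Table 7, including the null. On the 128-per-arm basis, restate the power, the four success probabilities and the MDV in Protocol 9.4.1 with the ranges given above. Say that the blinded dispersion is imprecise and show results over a range of k, for example 1.6 to 2.0. Rerun the effective sample sizes in Protocol Table 9 if they also used 1.6, which the protocol does not say.

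The cost is one rerun of the design calculation and slightly less favourable published figures. Sample size, prior, prior weight, the 95% rule and trial conduct stay as they are.

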5.2. Sample Size Sensitivity

The sample size in Section 5.1 is based on an expected reduction in this rate for subjects treated with mepolizumab. If the expected reduction with mepolizumab differ then, at the given sample size there will be an effect on the probability of success of the study.

[Table 2](#) illustrates this effect on probability of success of varying reductions in rates with mepolizumab, assuming the sample size remains constant at 128 subjects in mepolizumab arm and 128 subjects in placebo arm, excluding the additional 44 subjects to account for early withdrawals from study treatment.

Table 2 Probability of meeting the success criterion conditional on various assumed true treatment effects

Reduction	0.45	0.4	0.35	0
Probabilities of Success	94.6%	88.6%	80.0%	11.8%*

*The probability of success will equal with Type I error when there is no treatment effect for Mepolizumab compared with placebo.

In the [Table 2](#), the probabilities of meeting success are conducted under various assumed true treatment effects when overall event rate is fixed as 0.78 based on the blinded evaluation and dispersion is 1.6, e.g. when reduction is 40%, then the probability of success is calculated by the exacerbation rates for Mepolizumab 100mg SC and placebo as 0.585 and 0.975 p.a. respectively. Type I error is 11.8%, which is calculated when the event rate for each group is 0.78, adjusted dispersion is 1.6 based on analyses of blinded evaluation.

5.3. Sample Size Re-estimation or Adjustment

Blinded evaluation of exacerbation rates is planned for this study. A blinded evaluation of exacerbation rates for the purpose of sample size re-estimation will be done after 15 months of enrolment, or when 225 subjects have been randomized, whichever is earlier. If the exacerbation rates for the study are lower than planned, a sample size re-estimation may be conducted. Any subsequent change to the planned number of subjects randomized would be documented in a protocol amendment.

By the time of this protocol amendment, blinded evaluations of exacerbation rate were completed indicating the data deviate substantially from the assumptions made when we planned the trial, before the COVID-19 pandemic, thus supporting a protocol amendment to update the planned primary analyses without further adjustment of planned sample size.

6. SUPPORTING DOCUMENTATION

6.1. Appendix 1 Study Population Analyses

Unless otherwise specified, the study population analyses will be based on the MITT Analysis Set. A summary of the number of participants in each of the participant level analysis set will be provided.

6.1.1. Participant Disposition

A summary of the number of subjects included in each population will be produced.

The proportion of screen failures, the proportion who reported each reason for screen failure will be presented for the ASE population. The number of randomized subjects who did not receive treatment will be listed. The reason of Inclusion, Exclusion, Randomization Criteria is failed for screening will be summarized for ASE population. The deviations for these criteria will be presented as well on MITT analysis set.

The subject's completion status will be presented as percentage of withdrawals from the study as well as the reasons for withdrawal. The number and percentage of subjects who completed through Week 52 and who withdrew, including the primary reasons for withdrawal, will be displayed.

A summary of study treatment status will be provided. This display will show the number and percentage of participants who have completed the scheduled study treatment or have discontinued study intervention prematurely, as well as primary reasons for discontinuation of study intervention.

In addition, the subjects' study completion status and treatment status will be summarized by related to COVID-19 and not related to COVID-19 respectively.

The summary of study treatment impacted by COVID-19 will be provided.

Visits and assessments missed due to the COVID-19 pandemic, together with visits conducted remotely, will be listed.

The proportion of subjects in the MITT population at each centre will be presented.

A listing will be provided of subjects who interrupted or discontinued IP, including reason and date of interruption or discontinuation.

Subjects for whom the treatment blind was broken during the study will be listed.

A listing of planned and actual treatments will be provided for each subject by Site ID, and Investigator name.

6.1.2. Demographic and Baseline Characteristics

Demography

Demographic characteristics (age, sex, ethnicity, race, height, weight and body mass index) will be summarised and listed. For age group, it also will be categorised by group: 12-17 years, 18-29 years, 30-49 years, 50-64 years and ≥ 65 years.

Randomization stratification factor

Randomization stratification factor blood eosinophil count at screening (≥ 300 cells/ μL and < 300 cells/ μL) will be presented by treatment group. A shift table of differences between stratification factor and as Randomized (data entered into the IWRS system) will be produced.

Stratification factors (randomized and actual strata) will be listed for all subjects by treatment group.

Medical Conditions

The proportion of subjects who report medical conditions in each medical condition class will be presented, for current and past conditions separately. Current and past medical conditions will be listed.

Cardiovascular Assessment

A summary of the baseline cardiovascular assessment will be presented. The proportion of subjects who report a family history of medical conditions that may indicate predisposition towards cardiovascular conditions will be summarised.

Asthma History and Tobacco Use

Asthma history including duration of asthma (including derived age of onset), OCS use and exacerbations in the 12 months prior to Visit 1 will be summarised and listed.

Asthma disease characteristics and causes of exacerbations will be summarised and listed.

History of tobacco use will be summarised (i.e., non-smoker, former smoker).

Screening and Baseline Lung Function Tests

The following Screening (Visit 1) and (Visit 2) clinic lung function results will be summarised. Pre and post bronchodilator FEV1 will be listed in the same listing as the raw FEV1 listing in Section 4.3.2. The rest of the screening lung function results detailed below will be listed in a separate listing.

- Pre and post bronchodilator FEV1 (mL)
- Pre and post-bronchodilator percent predicted FEV1 (%)
- Reversibility (in mL and in %)
- Pre and post bronchodilator Forced Vital Capacity FVC (mL)
- Pre and post bronchodilator FEV1/FVC

